8. CLINICAL AND LABORATORY EVALUATIONS

Schedule of Assessments. See Appendix C for Study Calendar.

8.1 Pre-Registration Evaluations

NOTE: This section lists baseline evaluations that are required for registration. Evaluations should be performed within 4 weeks of registration unless otherwise indicated.

8.1.1 Required Pre-Registration Evaluations

- History and physical examination, including vital signs, weight, height and ECOG performance status determination.
- Complete blood count, including platelets and differential.
- Blood chemistry studies (may be obtained from whole blood or serum/plasma samples), including BUN, creatinine, electrolytes (K^+ , Na^+ , Cl^- , CO_2), glucose, calcium, Mg^{++} and liver function tests (total protein, albumin, total bilirubin, AST (SGOT), ALT (SGPT), and alkaline phosphatase), uric acid, and lactate dehydrogenase.
- Coagulation studies, including prothrombin time (PT), international normalized ratio (INR), and activated partial thromboplastin time (aPTT).
- Thyroid function tests, including thyroid stimulating hormone (TSH), free thyroxine, (FT4), anti-thyroglobulin antibody, thyroid peroxidase antibody, thyroid stimulating immunoglobulin, and ANA. Establishing baseline thyroid function and pre-existing thyroid auto- immunity is required, as an appropriate clinical standard prior to chemoradiotherapy for HNSCC as well as anti-PD1 therapy for HNSCC. However, normal thyroid function and absence of subclinical thyroid auto-immunity (example detectable anti-thyroglobulin antibody or detectable thyroid peroxidase antibody) are not eligibility criteria. If subclinical hypothyroidism is detected, treatment should be initiated according to standard practice. If subclinical thyroid auto-immunity is detected, the patient is still eligible.
- For women of child bearing potential: Urine or blood pregnancy test within 2 weeks of registration to rule out pregnancy. (Note, pregnancy test will be repeated within 3 days of initiating protocol treatment.)
- Baseline tumor measurements within 4-6 weeks prior to registration. Contrasted diagnostic CT scan for staging and baseline tumor measurements. In the rare case that a patient is not a candidate for contrasted diagnostic CT scan (e.g. history of allergic reaction to iodinated contrast despite premedication), MRI of the neck may be conducted for baseline tumor measurements. **Note:** when feasible, a baseline integrated PET/CT with diagnostic contrasted CT scan is preferred. Any scans or x-rays used to document measurable disease should be done as close to study entry as possible and within 4 weeks prior to registration.

- Evaluation by an otolaryngologist with endoscopy as indicated, within 8 weeks prior to registration. Endoscopy for oropharyngeal carcinoma may be performed as clinically indicated. Endoscopy is required for hypopharyngeal and laryngeal carcinoma.
- For oropharyngeal or unknown primary cases: HPV status must be known or established and recorded at baseline.
- Tobacco history assessment form (See Appendix A).

8.1.2 Recommended Pre-Treatment Evaluations

Note: This section lists baseline evaluations recommended but not required before the initiation of protocol treatment. These evaluations do not affect eligibility.

- An audiogram within 12 weeks prior to start of protocol treatment and 8 to 12 weeks after IMRT is complete
- Dental evaluation and if applicable, prophylaxis, within 12 weeks prior to the start of protocol treatment. Prior to treatment, patients should be evaluated by a dental professional and receive clearance to initiate radiotherapy. A delay of at least 10 calendar days from major oral surgery, including dental extractions, is recommended prior to first radiotherapy treatment.
- Patients should be provided with dental education including the risk for radiation-induced dental decay, methods for maintaining good oral hygiene, and use of prescription fluoride treatment. Appropriate oral hygiene includes the following: brushing teeth after each meal, flossing daily, the frequent use of oral rinses with Salt and/or Baking Soda (every two to four hours), and the daily use of prescription fluoride therapy.
- Nutritional Evaluation. It is strongly encouraged that all patients undergo an initial dietary assessment by a trained dietitian, prior to start of protocol treatment. Patients with weight loss and inadequate oral intake should be strongly considered for a feeding tube prior to initiation of therapy. For patients with adequate oral intake, the prophylactic placement of a feeding tube is at the discretion of the treating physician. Patients should be followed by dieticians routinely throughout the course of treatment. Dietary recommendations should include: recommended total caloric intake, recommended intake of protein, daily requirement for free water, and the appropriate use of

supplements. Should it become evident at any time during therapy that oral intake is inadequate, a feeding tube should be placed. Close monitoring by dieticians is important for patients with feeding tubes, particularly immediately after tube placement as patients often experience problems with enteral feeding or formulations. All patients who have a feeding tube placed should be referred to Speech and Language Pathology (SLP) for swallowing exercises to minimize disuse atrophy. In addition, post-treatment, it is critical to work with the SLP and dietitian to identify when it is safe and appropriate for patients to return to oral intake. Patients should be encouraged to wean themselves off their feeding tubes as soon as possible in order to maximize swallowing outcomes.

- Speech and Language Pathology (SLP). It is strongly encouraged that all patients undergo swallowing assessment and therapy prior to the start of protocol treatment. Swallowing assessment and therapy should be considered a critical component of care for all head and neck cancer patients undergoing concurrent therapy. Assessments should be done by a trained Speech-Language Pathologist. SLP should be consulted during treatment planning and should provide routine follow-up throughout the trajectory of the patient's treatment and recovery. The treating physician should communicate with SLP in order to coordinate care in those patients found to have significant swallowing abnormalities. Critical component of the swallowing evaluation should include: 1) identification of any swallowing abnormalities, 2) recommendations for further testing, 3) formation of a treatment plan, 4) dietary recommendations and 5) clear identifications of patients at risk for aspiration. Patients should be referred immediately for evaluation if any of the following "trigger symptoms" are identified: coughing or clear the throat before, during or after eating, inability to control food, liquids or saliva in the oral cavity, complaint of difficulty swallowing or food "sticking" in the throat, nasal regurgitation of food, or pocketing of food in the cheek.

8.2 Evaluations during treatment

8.2.1 Arm 1 (Cisplatin-IMRT followed by sequential pembrolizumab)

ARM 1, WEEKS 1-7 (During

concurrent cisplatin-IMRT)

Weekly:

Note: The following assessments will be performed weekly and may be performed on the day of or the day prior to cisplatin administration.

- History and physical examination.
- Vital signs, including weight.
- Toxicity assessment with attribution.
- Update of concomitant medications.

- Complete blood count, including platelets and differential.
- Blood chemistries (may be obtained from whole blood or serum/plasma sample), including creatinine, electrolytes (K+, Na+, Cl-, CO₂), calcium, Mg++ and liver function tests [bilirubin, AST (SGOT), ALT (SGPT), and alkaline phosphatase, total protein, albumin].

Every 3 weeks (Week 3 and Week 6):

Note: The following assessments will be performed every 3 weeks during concurrent cisplatin-IMRT and may be performed on the day of or the day prior to cisplatin administration. It is recommended that research blood should be coupled to the standard of care blood draw, to minimize needle sticks to the patient.

- Thyroid function tests (TSH, FT4).

Once (Week 6):

- Anti-thyroglobulin antibody, thyroid peroxidase antibody, thyroid stimulating immunoglobulin, and ANA.

ARM 1, WEEKS 8-31 (During sequential

pembrolizumab treatment): Every 3 weeks (Week 9, 12, 15, 18, 21, 24, 25, 30):

Note: The following assessments will be performed every 3 weeks, and may be performed on the day of or the day prior to pembrolizumab administration.

- History and physical examination.
- Vital signs, including weight.
- Toxicity assessment with attribution, including irAE assessment.
- Update of concomitant medications.
- Complete blood count, including platelets and differential.
- Blood chemistries (may be obtained from whole blood or serum/plasma sample), including creatinine, electrolytes (K+, Na+, Cl-, CO₂), calcium, Mg⁺⁺ and liver function tests [bilirubin, AST (SGOT), ALT (SGPT), and alkaline phosphatase, total protein, albumin] .
- Thyroid function tests (TSH, FT4).

Twice (Week 18, Week 30; these will be performed at the 4th and 8th doses of pembrolizumab, respectively):

- Anti-thyroglobulin antibody, thyroid peroxidase antibody, thyroid stimulating immunoglobulin, and ANA.

8.2.2 Arm 2 (Concurrent pembrolizumab, cisplatin and IMRT)

ARM 2, WEEKS -1 to +7 (During concurrent

pembrolizumab, cisplatin-IMRT) Weekly:

Note: The following assessments will be performed weekly starting Week -1, and may be performed on the day of or the day prior to pembrolizumab and/or cisplatin administration.

- History and physical examination.
- Vital signs, including weight.
- Toxicity assessment with attribution, including irAE assessment.
- Update of concomitant medications.
- Complete blood count, including platelets and differential.
- Blood chemistries (may be obtained from whole blood or serum/plasma sample), including creatinine, electrolytes (K+, Na+, Cl-, CO₂), calcium, Mg⁺⁺ and liver function tests [bilirubin, AST (SGOT), ALT (SGPT), and alkaline phosphatase, total protein, albumin].

Every 3 weeks (Week 3 and Week 6):

Note: The following assessments will be performed every 3 weeks during concurrent pembrolizumab, cisplatin-IMRT, and may be performed on the day of or the day prior to cisplatin/pembrolizumab administration. It is recommended that research blood should be coupled to the standard of care blood draw, to minimize needle sticks to the patient.

- Thyroid function tests (TSH, FT4).

Once (Week 6):

- Anti-thyroglobulin antibody, thyroid peroxidase antibody, thyroid stimulating immunoglobulin, and ANA.

ARM 2, WEEKS 8-25 (During sequential

pembrolizumab treatment): Every 3

weeks (Week 9, 12, 15, 18, 21):

Note: The following assessments will be performed every 3 weeks, and may be performed on the day of or the day prior to pembrolizumab administration.

- History and physical examination.
- Vital signs, including weight.
- Toxicity assessment with attribution, including irAE assessment.
- Update of concomitant medications.

- Complete blood count, including platelets and differential.
- Blood chemistries (may be obtained from whole blood or serum/plasma sample), including creatinine, electrolytes (K+, Na+, Cl-, CO₂), calcium, Mg++ and liver function tests [bilirubin, AST (SGOT), ALT (SGPT), and alkaline phosphatase, total protein, albumin].
- Thyroid function tests (TSH, FT4).

Twice (Week 9, Week 21; these will be performed at the 4th and 8th doses of pembrolizumab, respectively):

- Anti-thyroglobulin antibody, thyroid peroxidase antibody, thyroid stimulating immunoglobulin, and ANA.

8.3 Post-treatment Evaluations

8.3.1 Response Assessment

8.3.1.1 RECIST 1.1. Response assessment by RECIST 1.1 is required; integrated PET/CT interpretation is strongly recommended where available.

Twelve to 14 weeks following completion of cisplatin-IMRT (week 20-22 of protocol treatment), patients on both treatment arms will undergo diagnostic contrasted CT scan of the neck and chest, to assess treatment response according to RECIST 1.1. In the case where MRI of the neck was required for baseline tumor measurements, MRI of the neck should be repeated for response assessment, with non-contrasted diagnostic CT of the chest. Note: where available, an integrated PET/CT with contrasted diagnostic CT scans of the neck and chest is strongly preferred for response assessment.

8.3.1.2 Evaluation by an otolaryngologist with endoscopy as indicated.

8.3.1.3 The patient will be evaluated by the otolaryngologist 12-14 weeks following completion of cisplatin-IMRT (during weeks 20-22). Endoscopy for oropharyngeal or unknown primary carcinoma will be performed for response assessment as clinically indicated, and is at the discretion of the surgeon. Endoscopy is required for hypopharyngeal and laryngeal carcinoma. The surgeon will evaluate the need for primary site biopsy and/or neck dissection.

8.3.2 End of Treatment Visit(s): Week 33 (+/- 2 weeks) for Arm 1; Week 24 (+/- 2 weeks) for Arm 2. Patients will undergo the following procedures at the end of treatment visit:

- History and physical examination and performance status.
- Assessment for resolution of toxicities, including irAE, with attribution.
- Thyroid function testing (TSH, T3, FT4).
- Complete blood count, including platelets and differential.
- Blood chemistries (may be obtained from whole blood or serum/plasma sample), including BUN, creatinine, electrolytes (K+, Na+, Cl-, CO2), calcium, Mg++ and liver function tests (bilirubin, AST (SGOT), ALT (SGPT), and alkaline phosphatase, total protein, albumin).
- Audiogram assessment as indicated.

8.3.3 Surgical Consolidation

The necessity for and the timing of surgical consolidation will be determined by the surgeon. If patients undergo surgical consolidation, tumor tissue should be submitted for correlative study.

Primary Site

Surgery will be performed in the setting of resectable residual disease if the patient is considered a surgical candidate and:

- 1) Definitive radiotherapy was not completed, and radiographic or clinical evidence of persistent or progressive disease is established.
- 2) Biopsy-proven disease is demonstrated at the primary site and/or neck at least 8-12 weeks after completion of IMRT. In cases of residual disease at the primary site, the neck will always be dissected at the time of surgical salvage (if neck dissection was not previously conducted at post-protocol biopsy).

Surgical Management of the Neck

Neck dissection will be performed, if there is concern for residual disease. The extent of neck dissection will be determined by the surgeon. The consideration to perform less than radical procedures is strongly encouraged if oncologically safe. Note: the presence of residual disease at surgical consolidation, if performed within 24 weeks of completion of IMRT, will not constitute a progression event.

8.4 Long Term Follow Up

After the end of treatment visit, patients will be evaluated every 3 months for 21 months (+/- 2 weeks), then every 6 months (+/- 1 month) for one year, then annually (+/- 1 month) for two years, which will represent a total of 5 years from completion of IMRT. Thus, long-term follow-up evaluations will start approximately 6 months after completion of IMRT, and will include the following:

- History and physical examination and performance status.
- Vitals signs, including weight.
- Assessment for late toxicity, including dysphagia, xerostomia, gastrostomy tube dependence, pain, fibrosis and lymphedema within the head and neck, hypothyroidism, late autoimmune events.
- Thyroid function testing (TSH, FT4).
- Complete blood count, including platelets and differential.
- Blood chemistries (may be obtained from whole blood or serum/plasma sample), including BUN, creatinine, electrolytes (K+, Na+, Cl-, CO2), calcium, Mg++ and liver function tests (bilirubin, AST (SGOT), ALT (SGPT), and alkaline phosphatase, total protein, albumin)
- During the long term follow-up period, tumor assessments will be performed 6, 9, 12, 18, 24, 36, 48, and 60 months after completion of radiotherapy (+/- one month). The minimum protocol imaging requirement is: contrasted, diagnostic neck and chest CT at intervals specified above. More intensive imaging may be conducted per local practice.
- Swallowing assessments per local practice and as indicated by post-radiotherapy evaluation and patient-reported symptoms.
- Note: patients who have documented progression may discontinue scheduled study assessments and will be followed only for survival. Survival assessments will be performed every 6 months (+/- 2 months) by telephone contact and/or by evaluation of the Social Security Death Index or other public records.

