5.5 Duration of Treatment and Follow-up

Complete treatment includes the course of definitive radiotherapy with concurrent chemotherapy and a total of 8 doses of pembrolizumab. In the absence of treatment delays due to adverse event(s), treatment may continue until disease progression or until one of the following criteria applies:

- Intercurrent illness that prevents further administration of treatment,
- Unacceptable adverse event(s),

- Patient decides to withdraw from the study, or
- General or specific changes in the patient's condition render the patient unacceptable for further treatment in the judgment of the investigator.

Patients will be followed for progression and survival every 3 months for two years, then every 6 months for one year, then annually for two years after removal from study or until death, whichever occurs first. Patients removed from study for unacceptable adverse event(s) will be followed until resolution or stabilization of the adverse event.

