- j. These evaluations are strongly encouraged, but not mandatory. See section 5.4.13 for guidelines.
- k. Long term follow up assessments (examination, non-thyroid laboratories, adverse event/late toxicity assessments) should occur every 3 months for 2 years, then every 6 months for 3 years, for a total of 5 years from completion of IMRT. No specific requirements if patient is more than 5 years from study entry. If patient dies during follow-up, cause of death should be recorded.
- l. Women of child bearing potential are required to have a pregnancy test within 2 weeks of 1st study treatment to rule out pregnancy

- m. For oropharyngeal cases, p16 status must be established at the participating site, if not previously known before the screening process.
- n. Evaluation by an otolaryngologist with endoscopy. Endoscopy is not required for oral cavity carcinoma. Endoscopy for oropharyngeal carcinoma may be performed as clinically indicated. Endoscopy is required for hypopharyngeal and laryngeal carcinoma.
- o. Cisplatin should be administered on Monday, Tuesday, or Wednesday of each treatment week and may be given either before or after the radiation therapy fraction that is given on the same day. When cisplatin and pembrolizumab are administered on the same day in Arm 2, pembrolizumab should follow cisplatin.
- p. Thyroid auto-immunity will be monitored as specified in section 8.2.

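### Follow-up examinations are counted from an end-of-treatment visit that falls 9 weeks later in Arm 1 than in Arm 2, which contradicts the plan's other follow-up clocks and leaves a small difference between arms in examination before the 1-year PFS landmark

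*Combined protocol and SAP*

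**What the plan says.** The combined protocol and SAP gives several clocks for follow-up after treatment.

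- **Clinic examinations, Section 8.4:** "After the end of treatment visit, patients will be evaluated every 3 months for 21 months (+/- 2 weeks", then 6-monthly for one year and annually for two.
- **End-of-treatment visit, Section 8.3.2:** "Week 33 (+/- 2 weeks) for Arm 1; Week 24 (+/- 2 weeks) for Arm 2".
- **Start of long-term follow-up, also Section 8.4:** "long-term follow-up evaluations will start approximately 6 months after completion of IMRT", with a stated total of 5 years from IMRT and no distinction by arm.
- **Section 5.5:** "Patients will be followed for progression and survival every 3 months for two years", then 6-monthly for one year and annually for two, counted from removal from study.
- **Appendix C, footnote k:** examinations 3-monthly for 2 years, then 6-monthly for 3 years, "for a total of 5 years from completion of IMRT".
- **Tumor imaging, Section 8.4:** "tumor assessments will be performed 6, 9, 12, 18, 24, 36, 48, and 60 months after completion of radiotherapy (+/- one month". The requirement is the same in both arms: "The minimum protocol imaging requirement is: contrasted, diagnostic neck and chest CT at intervals specified above". Footnotes h and i of Appendix C use the same clock through month 24.

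Section 6.1.3.7 counts PFS from the start of treatment. Under Section 9, if both arms meet the criteria, the one with the higher observed 1-year PFS advances.

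**The concern.** A site cannot follow all of these clocks at once. If it follows the end-of-treatment anchor in Section 8.4, the two arms are examined at different times after radiotherapy because Arm 1 finishes pembrolizumab later. The selection rule compares observed 1-year PFS with no margin, and at 40 patients per arm one patient is worth 2.5 points. An extra scheduled examination shortly before the landmark in one arm gives that arm an additional chance to have a progression recorded in time to count. The trial is open-label, imaging is preferred to clinical examination but is not the only route (Section 6.2), and Section 8.4 allows extra imaging under local practice. A suspicious examination can therefore lead to a scan that dates a progression before one year.

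**Working it through.** **Week convention.** IMRT lasts 7 weeks (Section 5.4.1). If week w begins w − 1 weeks after IMRT starts, it begins w − 8 weeks after IMRT ends. This reproduces the plan's own equivalence in Section 8.3.1.1: weeks 20 and 22 give 12 and 14 weeks after IMRT. One month is taken as 52.18/12 = 4.35 weeks, and 3 months as 13.045 weeks.

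**Placing the visits and scans.**

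| | Arm 1 | Arm 2 |
|---|---|---|
| End-of-treatment visit, after IMRT | 33 − 8 = 25 weeks (5.7 months) | 24 − 8 = 16 weeks (3.7 months) |
| First 3-monthly examination, after IMRT | 8.7 months | 6.7 months |
| End of the schedule (21 + 12 + 24 = 57 months later) | 62.7 months | 60.7 months |
| Examinations near the landmark, weeks from IMRT start | 45.0, 58.1 | 36.0, 49.1 |
| 9-month scan, weeks from IMRT start | 46.1 | 46.1 |
| 12-month scan, weeks from IMRT start | 59.2 | 59.2 |
| One year from first treatment, weeks from IMRT start | 52.2 | 51.2 |

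In protocol week labels the examinations fall in weeks 46 and 59 (Arm 1) and weeks 37 and 50 (Arm 2). Arm 2's landmark is one week earlier because its first pembrolizumab dose precedes IMRT by a week (Section 5).

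**Consistency.** The 6-month start fits neither arm exactly and misses Arm 1 by almost 3 months. The 5-year total roughly fits Arm 2 but not Arm 1.

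**What is left before the landmark.** The last scheduled scan is the 9-month scan, at the same time in both arms. Arm 1's examination comes about a week before it; Arm 2's comes 49.09 − 46.135 = 2.955 weeks after it. Arm 1's next examination, with both 2-week windows at their earliest, is at 58.1 − 4 = 54.1 weeks. The 12-month scan, one month early, is at 54.8 weeks. Both fall after one year. So, on nominal dates, only Arm 2 has a scheduled examination between the shared scan and the landmark.

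**Size.** Assume exponential PFS with 1-year value S, so the weekly hazard is h = −ln(S)/52.18. The share of patients progressing in the extra interval is about S × (exp(2.955h) − 1).

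- S = 0.60 (the plan's reference value): h = 0.00979; 0.60 × (exp(0.0289) − 1) = 1.76 points. At 25-75% detectability: 0.44-1.32 points.
- S = 0.70: h = 0.00684; 0.70 × (exp(0.0202) − 1) = 1.43 points. At 25-75%: 0.36-1.07 points.

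**Selection.** Take two independent binomials with n = 40, Arm 1 at 0.70, Arm 2 at 0.70 minus the shift, and ties split. The chance that Arm 2 is picked is 48.6% to 45.9% with the S = 0.70 shifts, and 48.3% to 44.9% with the S = 0.60 shifts, against 50% with no shift. The second pair applies a shift from the higher hazard to arms with 70% PFS, so it is the pessimistic end.

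**Windows.** The 9-month scan may fall anywhere from 41.8 to 50.5 weeks after IMRT start. With both 2-week windows, Arm 2's examination may fall from 45.1 to 53.1 weeks. A late scan or a late examination removes the difference; an early scan enlarges it.

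**The case against.** The strongest counter-argument is that progression here is essentially an imaging endpoint, and the imaging is already synchronised. The first response scan and ENT evaluation fall 12-14 weeks after chemoradiotherapy in both arms, and later scans run from completion of radiotherapy. This stands, and it rules out a tempting stronger reading. From the different examination dates a reader might infer that tumor assessment itself is unequal, with Arm 2 covered to about 2 weeks before its landmark and Arm 1 only to about 7. If progression were found only at clinic visits, apparent 1-year PFS under the 60% reference would be about 64.3% in Arm 1 and 61.2% in Arm 2. The documents do not support that: with the common scans alone the figures are 63.7% and 63.0%. The remaining 0.6 points comes from Arm 2's PFS clock starting a week earlier, not from the visit schedule.

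A second argument is that Section 8.4 can be read harmoniously. Its 57 months reach 60 if counting begins about 3 months after IMRT, which would place examinations at 6, 9 and 12 months in both arms, as in the follow-up column of Appendix C. That may be the intention, but it requires ignoring the explicit end-of-treatment anchor and does not reconcile Section 5.5.

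Third, the 25-75% detectability has no source in the documents, and the windows are as wide as the effect. Both are fair; they limit how much weight the size estimate can carry, not the finding that the clocks disagree.

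**Conclusion.** The follow-up anchor is wrong as written. The end-of-treatment clock in Section 8.4 cannot be squared with that section's own start and total, with Section 5.5, or with footnote k, and this conclusion needs no modelling assumption.

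The consequence for the selection endpoint is small. It is confined to progression first detected at one nominal Arm 2 examination about 3 weeks after the shared 9-month scan. The estimate of about 0.4-1.3 points off Arm 2's 1-year PFS, and a selection chance of about 45-49% instead of 50%, rests on exponential PFS, a 60-70% 1-year rate, the assumed detectability and nominal dates. On those dates it runs against Arm 2. The one-week difference in PFS origin is a separate matter.

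**What to change.** In Sections 8.4 and 5.5, schedule every follow-up examination in months from completion of IMRT, at the same nominal months in both arms and coinciding with the scans at 6, 9 and 12 months. Remove end of treatment and removal from study as anchors for these examinations. Keep the end-of-treatment visits themselves; in Arm 1 the week-33 visit, at about 5.7 months, can serve as the 6-month visit. Reconcile the later intervals too: Sections 8.4 and 5.5 go to annual visits for the last two years, whereas footnote k stays 6-monthly for the last three.

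The cost is amendment wording and reprogrammed visit windows. Moving the anchor adds no visits: Arm 2 keeps seven 3-monthly examinations (months 6 to 24), and Arm 1 needs six after the week-33 visit. Whether the last years gain visits depends only on which interval is kept. The change does not alter the PFS time origin in Section 6.1.3.7.
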